13.12.4. LPCF Imputation

For outcome scales with code "3" a LPCF replacement will be introduced (Last Percentile Carried Forward) as far as previous follow-up evaluations exist. This method carries forward the actual status information of the patient population, using the percentile value with back transformation to raw scale, instead of last value carried forward. This approach was recently developed and recommended by O'Brien, Zhang and Bailey (2005) for the analysis of data from chronic, progressive diseases as dementia. According to their simulation study the calculated estimators should be negligibly biased by missing data. If no general change of patients over time occurs the method is more or less identical with LOCF (Last Value Carried Forward), if change occurs bias is minimized.

If no previous follow-up measurement exists, the outcome scale remains missing. It is important to note that the chosen multivariate test procedure (Wei-Lachin procedure) can handle partially missing single scales of type MCAR (missing completely at random).

13.13. Definition of study population

13.13.1. General Issues

Before the study is unblinded, a blind review will be performed. In this process, possible protocol violations will be classified as "severe", "major", "minor", or "none". Patients will be allocated to the individual data sets with regard to the classification of possible protocol violations. The analysis populations (Safety, ITT, and PP) will be listed individually in the final statistical analysis plan.

13.13.2. Safety Population

Safety population includes all patients who have had at least one dose of study medication and one contact with the Investigator afterwards. It will be used for safety analysis.

13.13.3. ITT Population (Full Analysis Set)

ITT population is defined as all patients who have no "severe" violation of entry criteria, had at least one dose of medication and at least one post-baseline observation of at least one primary efficacy criterion ("modified" ITT). This way ITT is defined in the sense of the "full analysis set" according to ICH E9 § 5.2. ("Analysis Sets") . ITT population will be used for all efficacy analyses.

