13.9. Sample Size Calculation

The power for this study is determined based on the following design specifications:

- (a) One-sided type I error defined as alpha = 0.05 (multiple level alpha, see section 13.7)
- (b) Type II error defined as $\beta = 0.2$ (Testpower 80%)
- (c) Design alternative effect size: Mann-Whitney statistic (MW) = 0.64 (medium-sized difference according to Cohen (Colditz, 1988); assuming a normal distribution the effect size MW may easily be re-expressed as the well-known Cohen effect size (Cohen, 1988) of a standardized difference (Cohen's d): MW = 0.64 means Cohen's d = 0.5)
- (d) Estimated correlations among the single outcome scales included in the global statistics $\rho = 0.4$)

Nonparametric sample size calculations within the framework of a multiple outcome approach (Wei-Lachin procedure- Wei and Lachin, 1984; Lachin 1992) was performed applying the validated software Nnpar 1.0 from idv Data Analysis and Study Planning, Krailling/Munich (see also Tang, 1989; Lachin, 1981). A good example for sample size calculation according to the Lachin approach (Wei and Lachin, 1984; Lachin 1992; Lachin, 1981) in multidimensional trials with neuroprotective agents is also given by Huang (2008).

Please note: further details of the effect size (Mann-Whitney statistic) are described in section 13.10, further details of sample size assessment are described in the separate document "Sample Size Assessment Based on a Multidimensional Efficacy Approach".

Based on the above design specifications, the total required sample size for the multivariate ensemble results in 30 patients per group (including 10% enhancement for usual "ambiguities", e.g., dropouts). With this sample size a "medium-sized" group difference (MW = 0.64) with regard to the multivariate outcome ensemble at month 3 and 6 can be detected with a power of 80%.

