The confirmatory analyses are performed with the ITT population according to the ICH Guideline E9 (full analysis set). Since the use of the per protocol set, however, maximises the opportunity for a new treatment concept to show additional efficacy in the analysis, and most closely reflects the scientific model underlying the protocol (see ICH E9, section 5.2.2), the supportive analysis by means of the per-protocol set will be regarded as of equal scientific importance (see also Schwartz 1967, Schwartz 1980, Senn 2007).

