13.12. Accounting for missing data

13.12.1. Missing Data Problems – General Considerations for a TBI Study

Missing data are a problem in every data analysis. Of course, there are always missing data of the type 'missing completely at random' (MCAR), which in principle will not bias the results; the analysis procedure should be able to cope with partially missing data of such a type. In many studies this type of data is treated by LOCF replacement (Last Observation Carried Forward) as far as there exist follow-up measurements at previous visits.

In a study like the one planned there might also be informatively missing data (missing not at random, MNAR): participants of the study died or are unable to complete the tests because of brain-related impairment. Neglecting these missing data might introduce bias.

A reasonable policy for minimizing bias in the case of informatively missing data (MNAR) is the replacement of these missing data by assigning the worst possible score, or a score worse than those observed. It should be noted that this strategy is only reasonable if rank-based robust procedures are used for the data analysis.

The worst rank imputation procedure was recommended by Lachin in his seminal paper about the missing data problem for data missing because of mortality when performing an exercise test (Lachin, 1999). This procedure was also used when analyzing nonfatal outcomes in studies where mortality was a problem (Lusben, 2002; McMahon, 2001). Recently a similar procedure has been proposed by the 'Traumatic Brain Injury (TBI) Clinical Trials Network' when designing the COBRIT study (Bagiella, 2010).

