Temkin (2007) included deaths with the worst rank for the significance tests of neuropsychological scales, but excluded deaths for the calculation of descriptive statistics (e.g., mean, SE estimates). Thus, significance tests reflect all patients with estimation of missing data while the descriptive statistics reflect only the actually observed assessments. We prefer not excluding deaths from descriptive statistics, since the study treatment with more deaths would artificially have better neuropsychological scores while a study treatment preventing deaths would be burdened by rather severe scores of survived patients. The use of robust descriptive statistics in this study allows the inclusion of worst rank scores for deaths also in descriptive analysis. This way, confirmatory analyses and descriptive analysis can be based on the same analysis data and contradictory results are avoided.

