13.13.4. Per Protocol Population (PP)

A sensitivity analysis will be performed for a per protocol (PP) data set as an exploratory approach. The PP population includes all patients who are eligible for ITT evaluation and who additionally do not show major protocol deviations. As noted in section 13.10, the supportive analysis by means of the per-protocol set will be regarded as of equal scientific importance as the ITT analysis, since it most closely reflects the scientific model underlying the protocol (see ICH E9, section 5.2.2).

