10. ANALYSIS SETS

ITT population will be used for all efficacy analyses. ITT population is defined as all patients who have no "severe" violation of entry criteria, had at least one dose of medication and at least one post-baseline observation of at least one primary efficacy criterion ("modified" ITT). This way ITT is defined in the sense of the "full analysis set" according to ICH E9 § 5.2. ("Analysis Sets").

A sensitivity analysis will be performed for a per protocol (PP) data set as an exploratory approach. The PP population includes all patients who are eligible for ITT evaluation and who additionally do not show major protocol deviations. The supportive analysis by means of the per-protocol set will be regarded as of equal scientific importance as the ITT analysis, since it most closely reflects the scientific model underlying the protocol (see ICH E9, section 5.2.2).

Safety population includes all patients who have had at least one dose of study medication and one contact with the Investigator afterwards. It will be used for safety analysis.

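### The ITT definition removes dosed patients who die, or cannot give any score, before Day 101, although the protocol's missing-data section says they must be kept at the worst rank

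*Protocol*

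**What the plan says.** **Analysis set.** Protocol 13.13.3 admits to ITT patients without a severe entry violation who "had at least one dose of medication and at least one post-baseline observation of at least one primary efficacy criterion". It labels the set modified ITT and assigns it to all efficacy analyses. SAP 10 repeats the definition.

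**Timing.** Protocol 11.1 and SAP 7 start the first treatment cycle on Day 31 and place the first post-baseline efficacy visit at Day 101. Neither schedule has an early-termination efficacy visit.

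**Missing data.** Protocol 13.12.1 identifies the informatively missing cases: "participants of the study died or are unable to complete the tests because of brain-related impairment. Neglecting these missing data might introduce bias". On deaths it says: "We prefer not excluding deaths from descriptive statistics". Protocol 13.12.2 codes each scale at each visit as valid (1), not completed for a TBI-related neurological reason (2) or not completed for another reason (3). Protocol 13.12.3 gives code 2 the worst possible score. Protocol 13.12.4 applies LPCF to code 3 and leaves the scale missing if there is no earlier follow-up value. SAP 12.1 repeats the three codes but attaches no worst-rank rule to them. Death has no code in either document.

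**Per-protocol set.** Protocol 13.10 names ITT as the confirmatory set, then adds that "the supportive analysis by means of the per-protocol set will be regarded as of equal scientific importance". Protocol 13.13.4 says "A sensitivity analysis will be performed for a per protocol (PP) data set as an exploratory approach" and also repeats the equal standing. So does SAP 10: "The supportive analysis by means of the per-protocol set will be regarded as of equal scientific importance as the ITT analysis".

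**The concern.** The set definition acts before the imputation rule. Worst-rank imputation can only reach patients who are in the analysis set, and entry to that set needs a score that an early death cannot supply. The patients whom Protocol 13.12.1 says must not be neglected are thus the ones the set definition removes. Protocol 13.12.1 itself argues that leaving out deaths flatters the arm with more of them.

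The arms have 30 patients each, so one or two such cases move the primary estimate visibly. If the rule is settled after unblinding, the choice could follow the result.

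The per-protocol wording is a second, smaller matter. That set is selected after randomisation (Protocol 13.15 removes patients with compliance below 80%), and the text gives it two incompatible standings.

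**Working it through.** **Inputs**
- From Protocol 13.9: "One-sided type I error defined as alpha = 0.05"; power 80%; "Design alternative effect size: Mann-Whitney statistic (MW) = 0.64"; correlation 0.4 between scales; 30 per group including 10% for dropouts and similar.
- From Protocol 13.4.2: nine scales in the ensemble.
- Assumed: 0 to 3 of 30 patients per arm die or give no score before Day 101. The documents give no such rate. Three equals the 10% allowance in number only, since that allowance is not a rate of death or inability.

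**The plan's own figure.** By Noether's formula, n per arm for one outcome = (1.645 + 0.842)² / (6 × 0.14²) = 52.6. Averaging K = 9 equally correlated outcomes multiplies this by (1 + 8 × 0.4)/9 = 0.467, giving 24.5, so 25. Dividing by 0.9 gives 28, within two patients of the stated 30. The documents do not state K; 18 components (nine scales at two visits) would give 26. The sample size is not in dispute. Losing three patients per arm lowers power only from 86% to 83% (K = 9), so the issue is what is estimated rather than power.

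**Who is affected**

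| Patient before Day 101 | Protocol 13.12 | Under the ITT definition |
|---|---|---|
| Dies | Kept, worst rank intended (no code provided) | Excluded |
| TBI-impaired, no score on any primary scale | Code 2, worst score | Excluded, unless a code-2 entry is an observation |
| TBI-impaired, at least one scale scored at Day 101 | Code 2 on the others, worst score | Included; the rule works |
| Leaves for a non-TBI reason, no follow-up | Code 3, stays missing | Excluded, but would contribute nothing anyway |

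**Size.** Let t and c be the early losses in the test and control arms, q₁ = 1 − t/30, q₀ = 1 − c/30, and m the Mann-Whitney value among observed patients. Deletion reports m. Ranking the lost patients below everyone observed, and tied with each other, gives

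MW = q₁q₀m + q₁(1 − q₀) + 0.5(1 − q₁)(1 − q₀).

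For example, 3/0 gives 0.9 × 0.64 = 0.576, and 3/3 gives 0.81 × 0.64 + 0.09 + 0.005 = 0.613.

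| Losses, test/control | Worst rank, m = 0.64 | Worst rank, m = 0.50 |
|---|---|---|
| 0/0 | 0.640 | 0.500 |
| 1/0 | 0.619 | 0.483 |
| 2/0 | 0.597 | 0.467 |
| 3/0 | 0.576 | 0.450 |
| 3/3 | 0.613 | 0.500 |
| 0/3 | 0.676 | 0.550 |

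Deletion reports 0.640 and 0.500 throughout. The 3/0 gap at m = 0.50 is 0.05, or 36% of the design effect (0.64 − 0.50 = 0.14).

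**Effect on the test.** A simulation of the averaged Mann-Whitney test (18 components, correlation 0.4, 30 per arm, m = 0.64, 3,000 runs) gave these one-sided rejection rates, deletion against worst rank: 89% against 37% for 3/0, 89% against 71% for 3/3, and 89% against 98% for 0/3.

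**Per-protocol wording.** Suppose, which the plan does not say, that success on either set were enough. The one-sided error would be 1 − P(Z₁ < 1.645, Z₂ < 1.645): 7.5%, 6.8% and 6.3% at assumed correlations of 0.80, 0.90 and 0.95. If the per-protocol set is a simple subset, the correlation is roughly the square root of the fraction retained, so 0.80 would mean excluding about 36% of ITT (1 − 0.80²).

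**The case against.** Much can be said for the plan. Entry to ITT needs only one observation on one primary criterion, and two of the criteria are clinician-rated scales, so many impaired patients would qualify and then be ranked worst on the rest. Scales are coded for every patient and visit, so a code-2 entry might itself be meant as an observation. Protocol 6.3.2 asks for reasonable effort to complete assessments in patients lost to follow-up. Entrants must be able to comply for the whole study, so early deaths may be few. The study calls itself exploratory. All of this stands and limits the number of patients affected, but none of it covers an early death.

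Three stronger readings are tempting and are not supported.

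- *All early dropouts are deleted when they should be ranked worst.* A code-3 dropout without follow-up stays missing under Protocol 13.12.4 whatever the set definition says.
- *The definition favours the test treatment.* The direction depends on which arm loses patients. Losses in the control arm alone make deletion understate the benefit.
- *The plan has two routes to success at full alpha.* Protocol 13.10 names ITT as confirmatory, the per-protocol analysis is also called supportive and exploratory, and no either-set rule is written.

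**Conclusion.** The contradiction is real and is in both current documents: the ITT definition excludes early deaths, and on a plain reading TBI-impaired patients with no score, whom Protocol 13.12.1 to 13.12.3 keeps at the worst rank. For one to three losses in one arm or three in each, the reported effect differs from the protocol's own worst-rank value by between −0.036 (0/3: 0.640 − 0.676) and +0.064 (3/0: 0.640 − 0.576). With no such losses there is no difference.

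These figures rest on the assumed losses, on an effect of 0.64 among observed patients, and on the lost patients ranking below everyone on every component. The actual size and direction cannot be fixed from the documents.

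The rule defines the primary analysis set, so it should be settled before unblinding. The per-protocol point is contradictory wording, and the 6.3–7.5% error is conditional on a decision rule that the plan does not contain.

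**What to change.** 1. **Protocol 13.13.3 and SAP 10:** drop the post-baseline-observation condition, so that the full analysis set is all randomised patients with at least one infusion or rTMS session. The exclusion for severe entry violations is a separate matter that this point does not turn on.
2. **Protocol 13.12.2 and SAP 12.1:** add death to the worst-rank code, and state that death or TBI-related inability takes the worst rank at every remaining visit.
3. **SAP 12:** restore the worst-rank rule. Without it, code 2 has no consequence in the SAP.
4. **Code 3 without follow-up:** say that these patients belong to the set but contribute no score under Protocol 13.12.4, and add a sensitivity analysis for them.
5. **Protocol 13.10, 13.13.4 and SAP 10:** delete the equal-importance wording. ITT alone decides, and per-protocol is a sensitivity analysis.

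While SAP 10 is open, reconcile it with SAP 13.5, which runs safety on ITT although SAP 10 assigns a safety population. With ITT as now defined, early deaths would also leave the safety tables.

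The cost is wording in two documents and a little more analysis work. The estimate may move in either direction.

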13.13.4. Per Protocol Population (PP)

A sensitivity analysis will be performed for a per protocol (PP) data set as an exploratory approach. The PP population includes all patients who are eligible for ITT evaluation and who additionally do not show major protocol deviations. As noted in section 13.10, the supportive analysis by means of the per-protocol set will be regarded as of equal scientific importance as the ITT analysis, since it most closely reflects the scientific model underlying the protocol (see ICH E9, section 5.2.2).

13.14. Homogeneity Analyses (Exploratory Interpretation)

Homogeneity analyses for baseline shall be performed based on the ITT population.

In addition to descriptive analyses robust nonparametric Mann-Whitney effects size measures and their two-sided 95% confidence intervals shall present an overview on demographic-anamnestic variables and on the primary efficacy criteria at baseline. This allows comparison of baseline variables across different scales and data types.

As benchmark for relevant baseline differences, a Mann-Whitney effects size measure of 0.36 and 0.64 respectively will be applied (referring to a standardized difference of 0.5 according to Cohen, which is regarded as a medium-sized difference).

In the case of heterogeneities, stratified analyses will be performed as second line analyses.

13.15. Compliance

Patients with compliance for the entire study below 80% for the treatments will be considered protocol violators and will not be included in the per protocol analysis.

13.16. Blind Review and Final Statistical Analysis Plan

A blind review of the data shall be performed within the framework of the requirements of the ICH Guideline E9. The statistical analysis plan will be finalized by the statistician before the decoding takes place. The analysis populations (Safety, ITT, and PP) will be listed individually in the final statistical analysis plan.

Formal records will be kept of when the statistical analysis plan was finalised as well as when the blind was subsequently broken.

13.17. Software Applied

Nonparametric sample size calculation was performed applying the validated software Nnpar 1.0 from idv Data Analysis and Study Planning, Gauting/Munich.

The data analysis will be performed in a validated working environment according to the requirements of the ICH-Guidelines E3 (1995). The software to be used for data evaluation will be described in the final statistical analysis plan.

14. ACCESS TO SOURCE DATA / DOCUMENTS

The Investigator will permit study-related monitoring, audits, IRB / IEC review and regulatory inspections, providing direct access to primary patient data (i.e. source data) which supports the data on the CRFs for the study, i.e. general practice charts, , appointment books, original laboratory records etc.

14.1. Source Data

Source data are defined as all information in original records and certified copies of original records of clinical findings, observations or other activities in a clinical study necessary for the reconstruction and evaluation of the study. Source data are contained in source documents (original records or certified copies).

14.2. Source Documents

Source documents are defined as original documents, data and records (e.g. hospital records, clinical and office charts, laboratory notes, memoranda, patient diaries or evaluation check lists, pharmacy dispensing records, recorded data from automated instruments, copies or manuscripts certified after verification as being accurate copies, microfiches, photographic negatives, microfilm or magnetic media, patient files, records kept at pharmacy, at the laboratories and at medico technical departments involved in clinical study).

Date: 040418

STUDY ID: CAPTAIN - rTMS

14.3. Direct Access

Direct access is defined as the permission to examine, analyse, verify and reproduce any records and reports that are important to evaluation of a clinical study. Any party (e.g. domestic and foreign regulatory authorities, the Sponsor and / or authorised representatives of the Sponsor such as monitors and auditors) with direct access should take all reasonable precautions within the constraints of the applicable regulatory requirements to maintain the confidentiality of patient identities and Sponsor proprietary information.

15. QUALITY CONTROL AND QUALITY ASSURANCE

15.1. Quality Control

Quality Control is defined as the operational techniques and activities, such as monitoring, undertaken within the quality assurance system to verify that the requirements for quality of the study related activities have been fulfilled.

Quality Control should be applied to each stage of data handling to ensure that all data are reliable and have been processed correctly.

15.2. Study Monitoring

Authorized, qualified Clinical Trial Monitor will visit the investigational site in regular intervals, established based on the needs of the project, *to* verify adherence to protocol and local legal requirements, to perform source data verification and to assist the Investigator in his study related activities

15.3. Quality Assurance

Quality Assurance is defined as the planned and systematic actions that are established to ensure that the study is performed and the data are generated, documented (recorded) and reported in compliance with Good Clinical Practice (GCP) and the applicable regulatory requirements.

Date: 040418

STUDY ID: CAPTAIN - rTMS

15.4. Inspection

An Inspection is defined as the act by an authority(IRB/IEC) of conducting an official review of documents, facilities, records and any other resources that are deemed by the authorities to be related to the clinical study and that may be located at the site of the study, or at the Sponsors and / or clinical research organisation facilities or at any other establishments deemed appropriate by the authorities.

